1.1. Synopsis

Title:	Toward Thriving Study
Grant Number:	N/A
Study Description:	A longitudinal clinical trial in a cohort of chronic pain to assess feasibility of a new behavioral intervention based on the principles of positive psychology. The study will recruit 20 participants, who will complete 4 timepoints (T1-T4). Participants will be consented at T1. T2 will be a kickoff meeting for all participants. After T2, participants will complete study intervention phase 1 (cultural probe kit) for three weeks. Next participants will participate in a facilitated workshop at T3, complete phase 2 of the intervention, followed by an exit interview at T4. Participants will complete a study survey at T1 and T4.
Objectives*:	The purpose of this pilot study is to introduce and test a positive psychology intervention meant to empower chronic pain patients and help support their resiliency and thriving.
Endpoints*:	
 Primary: Feasibility and acceptability of the behavioral intervention (cultural probe kit related activities). Percent (%) of participants engaging in the intervention between T1 and T4 Secondary: Change in PGIC between T1 and T4 Change in PROMIS Pain Interference between T1 and T4 Exploratory: Change in PROMIS 29 depression, anxiety sleep, fatigue between T1 and T4
Study Population:	Participants over the age of 18 with chronic pain
Description of Sites/Facilities Enrolling Participants:	This study will recruit patients at the Michigan Medicine. There will be no sites outside of the US.
Description of Study Intervention/Experimental Manipulation:	Participants will complete a cultural probe kit over 3-weeks. This kit is a design research tool, to prompt participants to document, map, journal, and reflect on various aspects of their daily lives
Study Duration*:	12 months
Participant Duration:	4 months

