5.2. Feasibility Study

We will collect data related to the number of participants approached and consented; the percentage consented who attend the facilitated workshop, the number of activities the participants at the workshop have completed, the number of participants who take part in the exit interview and the progress made towards goals set at the Sensemaking Workshop. We will also explore the intervention's potential to improve patient-reported outcomes including patient global impression of change (PGIC). Patient-reported outcomes will be measured before and after the intervention.

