5.2.2. Outcome

The primary outcome is the proportion of participants who attending the Sensemaking Workshop have completed at least 2 of the 3 reflective tools. The secondary outcomes are patient's belief about the efficacy of intervention (PGIC) and other symptoms including pain interference, depression, anxiety, and sleep, etc. The rate of patients being lost-to-follow-up will also be tracked to aid in appropriate design of a future randomized clinical trial.

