5.2.3. Hypothesis test and power analysis

Frequencies will be calculated related to feasibility data (e.g., number of participants approached, consented, and take part in the workshop). Descriptive statistics of patient-reported outcomes will be calculated before and after the intervention. Paired t-tests are used on patients' changes from T1 to T4. Wilcoxon test will be applied if departure from the assumption of normality. Hypotheses tests are two-sided performed at the 5% significance level. 95% confidence interval will be conducted. Power analysis for efficacy is based on t-tests.

6. Study Intervention Discontinuation and Participant Discontinuation/Withdrawal

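### PGIC is scheduled only at T4, so the secondary endpoint of T1-to-T4 change in PGIC and the paired test on it cannot be computed as written

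*Combined protocol and SAP*

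**What the plan says.** The secondary endpoints in section 1.1 include "Change in PGIC between T1 and T4", alongside PROMIS Pain Interference. The same section says "Participants will complete a study survey at T1 and T4" but does not list what the survey contains. Table 1 in section 1.3 does itemise the instruments: the PGIC row has a single mark, at T4, and the PROMIS row has marks at T1 and T4.

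Section 5.2 names PGIC among the patient-reported outcomes and then states: "Patient-reported outcomes will be measured before and after the intervention". Section 5.2.2 describes it differently: "The secondary outcomes are patient's belief about the efficacy of intervention (PGIC) and other symptoms including pain interference". Section 5.2.3 gives the analysis: "Descriptive statistics of patient-reported outcomes will be calculated before and after the intervention", followed by "Paired t-tests are used on patients' changes from T1 to T4", with a Wilcoxon test if normality fails. Nothing in section 5 makes separate provision for PGIC.

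**The concern.** A change from T1 to T4 needs a value at each time, and the schedule provides only the later one. Section 5.2 cannot be reconciled with Table 1, and the paired test in section 5.2.3 has nothing to pair for this outcome.

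At stake is one of the two secondary endpoints in the synopsis. With no stated summary, someone has to choose between a mean, a median and a responder proportion, and to choose a cut for the last. Nothing in the plan ensures that this happens before the data are seen. The text could also be read as asking for a PGIC at T1, which would record an impression of change before any intervention had been given.

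**Working it through.** The plan gives no figure for PGIC to reproduce, so the check sets the sections side by side and counts what the schedule delivers.

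**Scheduled values per participant (Table 1, section 1.3; N = 20 from section 1.1)**

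| Instrument | T1 | T4 | T1–T4 pairs |
|---|---|---|---|
| PROMIS | 1 | 1 | up to 20 |
| PGIC | 0 | 1 | 0 |

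**Step 1: the literal endpoint.** Change = (PGIC at T4) − (PGIC at T1). The second term is not collected, so the number of computable changes is 0 of 20.

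**Step 2: the test.** A paired t-test or signed-rank test needs within-person differences. PROMIS has up to 20; PGIC has none.

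**Step 3: would a T1 value repair it?** No. By its name the PGIC is already a rating of change. A rating taken before the intervention has no intervention-related change to describe, so subtracting it would not give a meaningful quantity.

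**Step 4: what remains.** Up to 20 single ratings at T4. If these were summarised as a proportion improved, the exact (Clopper-Pearson) 95% interval for x of n is:

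- lower limit = Beta quantile at 0.025 with parameters (x, n − x + 1)
- upper limit = Beta quantile at 0.975 with parameters (x + 1, n − x)

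The counts below are illustrative. The documents give no dropout figure; n = 16 assumes 20% loss before T4, 20 × (1 − 0.20) = 16.

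| x/n | Proportion | Exact 95% CI |
|---|---|---|
| 10/20 | 50% | 27.2% to 72.8% |
| 15/20 | 75% | 50.9% to 91.3% |
| 8/16 | 50% | 24.7% to 75.3% |
| 12/16 | 75% | 47.6% to 92.7% |

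These intervals show what a T4-only analysis could deliver. They do not measure the defect; the figure that does is the 0 pairs.

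**The case against.** The best defence is that the synopsis phrase is shorthand for the T4 rating of change over the T1-to-T4 period. Table 1 fits that reading, and so does section 5.2.2, which describes a judgement made after the intervention. No sentence names PGIC together with the paired t-test, so section 5.2.3 could be taken to cover only outcomes measured twice. A paired t-test is also arithmetically a one-sample test on changes, so the named test family could extend to a PGIC rating once a neutral value is fixed. The descriptive statistics promised in section 5.2.3 could cover a simple T4 summary. This is, finally, a 20-person single-arm pilot.

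Much of this is fair. The rating is not lost, a basic description at T4 is within the plan's general wording, and the risk that staff add a T1 PGIC is a possibility rather than something the plan orders. But the lenient reading repairs only the endpoint's name. Section 5.2 still says before and after for a group of outcomes that includes PGIC, the paired analysis still has no T1 value, and a one-sample version would need a neutral value that the plan does not give.

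**Conclusion.** The concern holds. As written, the endpoint and the only inferential method offered for it conflict with the schedule: 0 PGIC pairs against up to 20 for PROMIS. The endpoint is mis-defined rather than unmeasurable, because up to 20 T4 ratings will be available. The primary feasibility and acceptability outcomes and the PROMIS outcomes are untouched.

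The conclusion rests on taking Table 1 as the governing list of assessments, since it is the only place where instruments are assigned to visits. It needs no assumption about dropout or the PGIC response scale; those affect only the illustrative intervals. It should be fixed, but it does not threaten the study.

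**What to change.** 1. In section 1.1, restate the endpoint as the PGIC rating at T4, with the reference period stated (change since T1, if that is what the question will ask). Align section 5.2.2 with it.
2. In sections 5.2 and 5.2.3, confine the before-and-after statements and the paired t-test or Wilcoxon test to the PROMIS scales.
3. Leave Table 1 as it is; do not add a PGIC at T1.
4. Name the PGIC version and its response categories.
5. Specify a single-timepoint analysis: the full distribution of T4 ratings with the number of raters. If the chosen version has a neutral category, which is an assumption here, also report the proportion improved, using a cut fixed in advance, with an exact 95% CI. A one-sample signed-rank test against the neutral category is optional.

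The cost is wording in sections 1.1, 5.2, 5.2.2 and 5.2.3. No data collection, visits or participants are added.

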1.2. Schema

[figure not shown]

Figure 1 Study Schema

1.3. Schedule of Activities (SOA)

Table 1 Study SOA

	Screening	T1	T2	T3	T4
Screening	x				
Consent		x			
Demographics		x			
PROMIS 29-+ 2		x			x
PGIC					x

Chronic Pain Conditions		X			
Facilitated Interview			x		x

2. Introduction

2.1. Objective

The purpose of this pilot study is to introduce and test a positive psychology intervention meant to empower chronic pain patients and help support their resiliency and thriving.

2.2. Specific Aims

Testing the efficacy of a custom-designed set of reflective tools (plus interactive workshop) to empower chronic pain patients and help them envision a personal path to thriving.

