3.4. Strategies for Recruitment and Retention

3.4.1. Methods of Recruitment

Participants will be screened and recruited through Michigan Medicine via the following methods:

1. In-person recruitment through Back and Pain Center (B&PC)
2. Umhealthresearch.com
3. Data direct queries
4. Flyers in clinic across Michigan Medicine
5. B&PC new patient registry APOLO HUM00041820

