4.3. Phase 2 and Exit Interview (T4)

Participants will end the study with 3-weeks of at-home activities and an exit interview about their experience. T4 may be completed in-person or virtually and maybe recorded.

5. Statistical Design and Analysis

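### The only stated specific aim is to test efficacy, but the primary endpoints are feasibility and acceptability and a single group of 20 cannot establish efficacy; the aim should be reworded

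*Combined protocol and SAP*

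**What the plan says.** Section 2.2 (Specific Aims) contains a single aim: "Testing the efficacy of a custom-designed set of reflective tools (plus interactive workshop) to empower chronic pain patients", and to help them picture a route to thriving. It names no instrument, and neither feasibility nor acceptability appears.

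The rest of the plan is built around something else:

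- The synopsis (1.1) describes "A longitudinal clinical trial in a cohort of chronic pain to assess feasibility of a new behavioral intervention" with 20 participants. Its primary endpoint is "Feasibility and acceptability of the behavioral intervention (cultural probe kit related activities". PGIC and PROMIS pain interference are secondary; the other PROMIS domains are exploratory.
- Sections 5.1.2 and 5.2.2 name the primary outcomes: participants' assessment of the tool and the overall experience, and the proportion of workshop attendees who completed at least 2 of the 3 tools. The 80% hypotheses in 5.1.1 and 5.2.1 correspond to these.
- Everyone follows the same path: "T2 will be a kickoff meeting for all participants", "After T2, participants will complete study intervention phase 1 (cultural probe kit) for three weeks", then a workshop, and "Participants will end the study with 3-weeks of at-home activities and an exit interview about their experience".
- "Participants will complete a study survey at T1 and T4". Section 5.2.3 plans paired t-tests (Wilcoxon if not normal) on T1 to T4 change, two-sided at 5%, with 95% confidence intervals. It closes by saying that an efficacy power analysis rests on t-tests, without giving one.
- Section 5.2 says the potential to improve patient-reported outcomes will be explored. Section 5.2.2 tracks loss to follow-up to help design a later randomized trial.

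**The concern.** The one stated aim has no primary endpoint, and the primary endpoints have no stated aim. The aim also asks for a conclusion that an uncontrolled cohort cannot give. Nothing in the plan warns that T1 to T4 change must not be read as efficacy. A significant paired test could therefore be presented as having met the study's only aim, while the questions the study is set up to answer would not appear among its aims at all.

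**Working it through.** **1. Aim against endpoints.**

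| Place | What it is about |
|---|---|
| 2.2, the only aim | Efficacy |
| 1.1, study description | Feasibility |
| 1.1, primary endpoint | Feasibility and acceptability |
| 5.1.1 and 5.1.2 | Acceptability (80% hypothesis, primary outcome) |
| 5.2.1 and 5.2.2 | Feasibility (80% hypothesis, primary outcome) |
| 1.1 and 5.2.2, PGIC and symptom scores | Secondary or exploratory |
| 5.2.3, last sentence | Power for efficacy |

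Section 2.2 and the last sentence of 5.2.3 are out of line with the other rows.

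**2. What the paired test can show.** Let D be a participant's T4 score minus T1 score, and write the mean of D as τ + ν. Here τ is the effect of the intervention and ν is everything else: natural course, regression to the mean, other care, expectation.

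- The paired t-test has the null hypothesis τ + ν = 0. The Wilcoxon test likewise tests for no shift.
- Efficacy is a statement about τ alone.
- With no comparator, nothing estimates ν, so τ is not identified, whatever the p-value or sample size.

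A nonzero ν is plausible here. Recruitment includes the "B&PC new patient registry", and the criteria in 3.1 and 3.2 do not require stable pain treatment. No figure for ν is needed for the argument.

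**3. The plan's own figure.** The sample size of 20 cannot be reproduced, because no effect size, SD, power or dropout rate is given with it.

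**4. What 20 participants can deliver.** The 95% confidence interval for a mean change has half-width t(0.975, n−1) × SD / √n, where SD is the standard deviation of the change.

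- n = 20 (synopsis): 2.093 / 4.472 = 0.468, or 0.47 SD.
- n = 16 (assumed 20% loss, 20 × 0.8 = 16): 2.131 / 4 = 0.533, or 0.53 SD.

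This applies to scores taken at both T1 and T4, which in Table 1 means PROMIS-29+2. Table 1 lists PGIC at T4 only, so it has no paired change.

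**5. Would a comparator within 20 rescue the aim?** Normal approximation, two-sided 5%, assumed standardized differences d between arms:

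- Number per arm for 80% power = 2(1.960 + 0.842)² / d²: 175 for d = 0.3, 63 for 0.5, 25 for 0.8.
- Power with 10 against 10 = Φ(d√5 − 1.960): about 10%, 20% and 43%.

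Over this assumed range a controlled efficacy test is out of reach at this size. The realistic change is to the aim.

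**The case against.** The strongest reply is that this is an openly labelled pilot. A single cohort of 20 is an ordinary pilot design, 5.2 speaks of exploring, 5.2.2 ranks symptom outcomes as secondary and points to a future randomized trial, and 5.2.3 already plans descriptive statistics and confidence intervals. All of that stands. It limits the point to wording, but it also shows that 2.2 departs from the plan's own intent.

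A second reply is that efficacy in 2.2 may mean empowerment as participants describe it, since the T4 interview asks whether the intervention seems potentially effective and could promote positive emotions and resilience. This is fair: the link from the aim to the paired tests is an inference from the efficacy wording in 5.2.3. But perceived potential is part of the acceptability hypothesis and is not a test of efficacy. Table 1 identifies no measure of empowerment, and that reading would be just as uncontrolled.

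Three stronger readings are tempting and are not supported:

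- A reader might infer that the design is wrong and needs a control arm. The primary hypotheses do not require one.
- A reader might infer that the sponsor intends to claim efficacy. No section says that T1 to T4 change will be attributed to the intervention; the risk is only that the aim leaves room for it.
- A reader might infer from 8.1.2 that an efficacy stop is planned. The bullet is one item in a generic list of circumstances that may warrant stopping, and no interim analysis is described. Similarly, the text under the 7.1 heading concerns only screening, consent and the survey.

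**Conclusion.** The point holds as an inconsistency of wording with a consequence for what may be concluded. The sole aim is one the design cannot meet, and the primary endpoints are missing from the aims. The attribution argument rests on the absence of a comparator. That is read from the text as a whole: no section calls the study single-arm, and the schema figure is not available in the text reviewed. The argument does not depend on any assumed effect size. The precision figures (0.47 and 0.53 SD of change) depend on 20 completers and on an assumed 16, respectively. The acceptability and feasibility hypotheses and their analysis are unaffected, so severity is low.

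**What to change.** 1. Reword 2.2, for example:

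> To assess the feasibility and acceptability of the reflective tools and workshop (hypotheses in 5.1.1 and 5.2.1), and to estimate T1 to T4 change in patient-reported outcomes with 95% confidence intervals. No conclusion on efficacy will be drawn from this single-group study.

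2. In 5.2.3, replace the closing sentence on efficacy power with the expected precision: 95% confidence interval half-width 0.47 SD of change with 20 completers, 0.53 SD with an assumed 16. Deleting only the efficacy label would not be enough, because it would leave a power analysis announced but not given. Add that any paired-test p-values are exploratory and are not evidence of efficacy.

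3. Reconcile the heading of 7.1 and the efficacy bullet in 8.1.2 with the new aim.

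The cost is text edits in four places and a more modest stated aim. No participants, visits, data collection or primary analyses change.

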2.3. Background

'Large studies in Europe, North America, Australasia, and other regions disclose that one in five of the adult population suffers from chronic moderate to severe pain¹ , yet there are societal misconceptions about what it means to live with chronic pain. Chronic pain sufferers encounter frequent barriers and few supports to help them live meaningful lives. This project has the potential to provide support to patients through positive psychology methods.

2.4. Methodology

Participants will be using a cultural probe kit, a design research tool, to prompt participants to document, map, journal, and reflect on various aspects of their daily lives. During an interactive, in-person workshop, participants will review and synthesize the contents of their probe kit and set goals for themselves. The workshop, which takes place after participants have completed three weeks of at-home activities, will be facilitated in small groups by a designer and psychologist team. Participants will end the study with 3-weeks of at-home activities and an exit interview about their experience. Specific instructions, as delivered in each week of the probe kit materials, as well as plans for the kickoff meeting, workshop and exit interview, follow.

3. Study Population

3.1. Inclusion Criteria

- Persistent or recurrent pain lasting longer than 3 months
- Age 18+
- Able to read and write English

3.2. Exclusion Criteria

- Cancer
 - History of any bone-related cancer or cancer that metastasized to the bone
 - Currently in treatment for any cancer or plan to start cancer treatment in the next 12 months
 - History of any cancer treatment in the last 24 months
- Active substance abuse
- Uncontrolled depression or psychosis
- Visual or hearing difficulties that would preclude participation
- Individuals started receiving disability or compensation within the past year, or currently involved in litigation
- Current/planned (in the next 2 years) enrollment in another study of a device or investigational drug that would interfere with this study, this may include participation in a blinded trial.
- Any other diseases or conditions that would make a patient unsuitable for study participation as determined by the site principal investigators. This would include but not be limited to severe psychiatric disorders, active suicidal ideations or history of suicide attempts, and an uncontrolled drug and/or alcohol addiction)

3.3. Screen Failures

Screen failures are defined as participants who consent to participate in the clinical trial but are later found to be ineligible. A minimal set of screen failure information is required to ensure transparent reporting of screen failure participants, to meet the Consolidated Standards of Reporting Trials (CONSORT) publishing requirements and to respond to queries from regulatory authorities. Minimal information includes demography, screen failure details, eligibility criteria, and any serious adverse event (SAE).

3.4. Strategies for Recruitment and Retention

3.4.1. Methods of Recruitment

Participants will be screened and recruited through Michigan Medicine via the following methods:

1. In-person recruitment through Back and Pain Center (B&PC)
2. Umhealthresearch.com
3. Data direct queries
4. Flyers in clinic across Michigan Medicine
5. B&PC new patient registry APOLO HUM00041820

3.4.2. Recruitment and Enrollment

Participants will be tracked and screened using REDCap, a HIPAA compliant electronic data capture system. Those patients who meet eligibility criteria will be consented electronically through REDCap. They will then be asked to complete a study survey via REDCap and scheduled for future visits.

3.4.3. Incentives

Participants will be paid up to \$250. They will receive \$150 for completing the workshop (T3) and associated intervention phase 1 kit and \$100 for completing the exit interview and associated phase 2 activities

4. Study Intervention

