5.2.1. Hypothesis

≥80% of participants attending the facilitated workshop will have completed at least 2 of the 3 reflective tools.

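### The primary feasibility outcome in section 5.2.2 measures kit completion that is itself paid for, and its attendee-only denominator can overstate completion among those who consented

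*Combined protocol and SAP*

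**What the plan says.** Section 3.4.3 (Incentives) opens with "Participants will be paid up to" $250. Of this, $150 is earned "for completing the workshop (T3) and associated intervention phase 1 kit" and $100 "for completing the exit interview and associated phase 2 activities". The $150 is a single item. It is not split between attendance and the kit, completion is not defined, and there is no rule for someone who attends with a partly finished kit.

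Section 5.2.1 gives the feasibility hypothesis as 80% or more "of participants attending the facilitated workshop will have completed at least 2 of the 3 reflective tools". Section 5.2.2 makes the corresponding proportion among workshop attendees the primary outcome.

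Section 5.2 also lists "the percentage consented who attend the facilitated workshop" among the feasibility data, with no criterion attached. Its count of completed activities is described for participants at the workshop, so no tool count is planned for those who miss it.

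The synopsis (section 1.1) words the primary endpoint differently, as the percentage "of participants engaging in the intervention between T1 and T4". It also gives the size: "The study will recruit 20 participants". There is one arm.

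**The concern.** Two features of the design affect what the 80% figure means.

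First, the numerator. The behaviour being counted, finishing the tools, is largely the behaviour being paid for. With no comparison group, the pull of the payment cannot be separated from the intervention's own burden and appeal. Those are what a feasibility study wants to learn about, and section 5.1 treats low burden as a property to be shown. Nothing in section 5.2 tells the reader that the result is conditional on this payment.

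Second, the denominator. Only people who come to T3 are counted. Someone who does few of the tools and then misses the workshop drops out of the calculation instead of counting as a non-completer. This would be so without any payment. Section 6.2 adds another route: the investigator may withdraw a participant for significant non-compliance with the intervention, which could also happen before T3.

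At stake is whether a result of 80% or more can be carried into the future randomized trial that section 5.2.2 mentions.

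**Working it through.** The plan gives no expected completion rate, attendance rate or incentive effect, so there is no stated figure to reproduce. The check has three parts.

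**1. Overlap of payment and outcome**

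- Share of the maximum payment tied to the T3 workshop and kit: 150/250 = 60%.
- Paid for (section 3.4.3): completing the workshop and the Phase 1 kit.
- Measured (section 5.2.2): at least 2 of 3 tools completed, among workshop attendees.

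Kit completion feeds the numerator and attendance defines the denominator, so the payment touches both. One step is inferred: the documents do not expressly equate the three reflective tools with the Phase 1 kit. Section 4.2 describes three weeks of kit activities followed by a workshop that reviews the kit, which makes this the natural reading.

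**2. Effect of the attendee-only denominator**

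Input from the plan: 20 participants. Assumed: C of the 20 complete at least two tools, all C attend T3, and a fraction *a* of the 20 − C non-completers attend. Then

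attendee rate = C / (C + (20 − C) × a), and all-consented rate = C / 20.

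The first is a ratio of expected counts.

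| C (all-consented rate) | a = 1 | a = 0.75 | a = 0.5 | a = 0.25 | a = 0 |
|---|---|---|---|---|---|
| 12 (60%) | 60% | 67% | 75% | 86% | 100% |
| 14 (70%) | 70% | 76% | 82% | 90% | 100% |
| 16 (80%) | 80% | 84% | 89% | 94% | 100% |

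For C = 14 and a = 0.5: 14 / (14 + 6 × 0.5) = 14/17 = 82%.

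In whole people, the 80% line is crossed as follows:

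- C = 14: with 3 of 6 non-completers attending, 14/17 = 82%, which passes. With 4 of 6, 14/18 = 78%, which does not.
- C = 12: with 3 of 8 attending, 12/15 = 80%, which passes. With 4 of 8, 12/16 = 75%, which does not.

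The all-consented rate stays at 70% or 60% throughout. The bias needs non-completers to attend less often than completers. If instead 2 of 14 completers were absent and all 6 non-completers came, the attendee rate would be 12/18 = 67%, below the true 70%.

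**3. Precision at this size**

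Exact 95% intervals are wide: 14/20 gives 46% to 88%, and 12/14 (86%) gives 57% to 98%. With all 20 counted and a true rate of 70%, the chance of seeing 16 or more completers is 0.24. A shift of a few people in the denominator is therefore enough to change which side of 80% the estimate falls on.

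**The case against.** A reader might infer that the payment discourages people with unfinished kits from attending. The documents do not support that. Section 3.4.3 does not say that an unfinished kit forfeits the $150, and the same sum rewards attendance, so it could equally bring partial completers in and lower the attendee rate.

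A reader might also conclude that the payment is shown to inflate the result. It is not, because the documents give no completion rate without payment. One can assume a lift: with all 20 attending, the chance of 16 or more completers is 0.118 at a true rate of 65%, 0.630 at 80% and 0.830 at 85%. This only restates the assumed lift, leaves selection out by fixing the denominator at 20, and uses a point-estimate pass rule that the plan does not state.

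Nor does it follow that the 80% criterion says little about feasibility. Section 5.2 also collects numbers approached and consented, attendance among those consented, and exit-interview participation. Section 5.2.2 tracks loss to follow-up, and section 5.1 asks about ease and burden separately. Selective absence from T3 could be suspected from the attendance figure. If the future trial paid on the same terms, completion under payment would be a relevant quantity for it. Paying for tasks rather than visits is also a legitimate design choice.

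These points limit the claim but do not remove it. Neither the attendance percentage nor loss to follow-up shows how many tools the absentees completed, and nothing in the plan says that the primary proportion was obtained under payment for the behaviour it counts.

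**Conclusion.** The point holds in a limited form. The outcome in section 5.2.2 is completion under contingent payment, given the natural reading that the reflective tools are the Phase 1 kit. This is a limit on interpretation whose size cannot be estimated from the documents. Any effect of the payment on who attends T3 is of unknown direction.

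The attendee-only denominator is a separate weakness and can be illustrated: 82% against 70% when 14 of 20 complete, all 14 attend and half of the other 6 do. Those attendance values are assumptions. With equal attendance in both groups the difference disappears.

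The wording *primary outcome* applies to section 5.2.2, since the synopsis defines its endpoint as engagement. This is an inexpensive improvement and not a flaw that undermines the study.

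**What to change.** 1. In section 3.4.3 and the consent form, keep the $150 but make it payable for attending T3 whatever number of tools is finished, and tell participants so at consent. The T4 payment need not change for this outcome.
2. In sections 5.2 and 5.2.2, record the number of tools completed for every consented participant, including those who miss T3. Report the proportion completing at least 2 of 3 among all consented participants beside the attendee-based rate. Where a count cannot be obtained, say how many are unknown and count them as not completed.
3. If the payment stays tied to the kit, define completion for payment and for the outcome, and state that the 80% result is completion under contingent payment.

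Cost: changes of wording, no rise in the total paid, and a short query to participants who miss T3, whom section 6.3 already requires the site to contact. The downside is that completion may be somewhat lower and the workshop, which works from the kit contents, may have less material.
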